The second step of recruitment: The subjects of the study will be selected during c-section by purposive sampling and only those subjects who will fulfil perioperative criteria of the study will be selected. The primary surgeons of the C-section will be 2nd and 3rd-year residents of Lady Willingdon Hospital. If dense adhesions will be encountered during opening the peritoneal cavity or before the separation of bladder flap, the primary surgeons will hold the operation and call the principal surgeon (Assistant [name] and Gynaecology) to carry out adhesiolysis and complete the operation. The Principal surgeon will examine the adhesions and enrol the subjects in the study and perform randomization according to the random number envelop if perioperative criteria for adhesions will be fulfilled. (See [Entry Form](#))

The same Principal surgeon will recruit subjects after carrying out grading of adhesions, perform adhesiolysis and complete the operation with primary surgeons to avoid bias.(See [Fig 1](#))

Randomisation procedure

The Principal surgeon will randomize the calculated sample size into cysto-inflation and control groups by parallel assignment. They will write the random numbers (downloaded from the internet) on closed envelopes with the assigned groups inside. The closed envelopes will be serially placed with the smallest number uppermost, in random number file. The file will be kept in the safe custody of theatre in-charge nurse before starting recruitment for the study. If the women will fulfil the eligibility criteria, the Principal surgeon will recruit her in the study. The theatre in charge nurse will take out uppermost envelope from the subject's file. She will be open the envelope and disclose the group to the principal surgeon. Then, she will close the envelope again and place it below all the envelopes. The theatre staff nurse will also provide the setup for cysto-inflation. At the end of the operation, she will get the Entry Form signed by the Principal surgeon and hand it over to the study team. The study team medical officers in the theatre will enter the random number of each subject on her documents including Hospital Admission File, Consent Form, Trial Entry Form and Outcome Form.

Blinding

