there while the surgeon holding the tubing will inflate the balloon of the urinary catheter with 10cc distilled water. The theatre attendants will then correct the position of the patient again to straight leg position. The urinary catheter will be kept elevated as long as the patient will be draped with sterilized sheets for operation by the other surgeon. Then, the catheter end near the urinary port will be fixed to the patient sheet in front of the thigh to carry out cystinflation conveniently and attached to the urine bag for drainage.

Adhesiolysis

If adhesions will be encountered during opening the peritoneal cavity or before the separation of bladder flap, the primary surgeons will hold the operation and call the principal surgeon to carry out adhesiolysis and complete the operation. The Principal surgeon will grade the adhesions according to Tulandi's classification and if the woman will fulfil perioperative criteria for adhesions, the Principal surgeon will enrol her in the study as subject and perform randomization into cystoinflation and control groups according to her random number envelope. Adhesiolysis will be performed with the inflated bladder in cystoinflation group, and with the empty bladder in the control group.

Cystoinflation group: The adhesiolysis in cystoinflation group will be performed by bladder retro-fill. Cystoinflation (bladder retrofill) will require normal saline drip and a 60cc bladder wash syringe and an artery clip. In cystoinflation group, the bladder will be retro-filled with 300cc saline by the assigned house officer under strict aseptic measures at the rate of 60cc in one minute. Meanwhile, the principal surgeon will identify the margins of the bladder among adhesions. The catheter will be clamped with an artery clip after filling the bladder with 5 fillings of the syringe. The surgeon will stretch the adhesions by upward traction on the surface of the uterus with a sponge and counter-traction on adhesion with elices forceps or sponge and perform adhesiolysis by sharp dissection with a fine dissecting scissor. The adhesiolysis will be performed until the bladder surface can easily be pushed down. Thereafter, the house officer will attach the urine drainage port of the catheter with the tubing of the urine bag and remove the artery clip to empty the bladder. The surgeon will then push the bladder downward with Doyen's retractor to improve visualization in the surgical field and complete the C-section.

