Control group: The subjects assigned to the control group will undergo no intervention. The Principal surgeon will perform adhesiolysis by the same traction counter-traction method with urinary catheter put on free drainage throughout the C-section.

If there will be a suspicion of bladder injury in either group, it will be confirmed by performing the retrograde dye test with methylene blue and injury will be repaired by the Principal surgeon.

Crossover

There is no possibility of crossover in this study as subjects will be selected during operation and the women who refuse to be included in either group preoperatively will be excluded from the study before group assignment.

Data collection procedure

Data will be collected at the time of admission (baseline), during surgery, on the 3rd postoperative day, at the time of discharge from the hospital and the end of three month follow-up period (for those enrolled in the study). The subjects will be advised to report for any postoperative fever or micturition problem during follow-up. Their visits will be recorded on follow up form by the study team medical officers specifically trained in correctly interpreting the problems of the subjects and filling the outcome form (See [Outcome](#) Form).

Baseline Data

The entry form will include baseline data consisting of demographic features and characteristics of the subjects recruited in the study. The demographic features will include age, gestational age, parity, socioeconomic status, and the number of previous C-sections. The other characteristics will be the score of adhesions and preoperative postmicturition bladder volume. The allotted random number will be entered in entry form of the subject and will be signed and kept in a locked place by study team manager in the theatre. (See [ENTRY FORM](#))

Outcome

Primary outcomes will be the bladder injury rate, the extent of the injury, operative time, blood loss and proportion of subjects receiving blood transfusion.

The bladder injury: The bladder injury will be detected by direct observation during surgery. The suspected bladder injury will be confirmed with the dye test and will be reported as the bladder injury rate and extent of injury.

- A. Bladder injury rate will be recorded as the percentage of subjects with bladder injury in each group.
- B. The extent of the injury will be analyzed by the size, site and depth of injury.

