 - i. The size of the injury will be measured in centimetres with a sterilized scale.
 - ii. The site of injury can either be the dome of the bladder, the posterior bladder wall, the trigone or one or both ureters.
 - iii. Depth of injury will be taken as layers involved i.e. either involving muscular layer partly or completely with intact mucosa or full depth injury (perforation).
 - iv.

Operative Time: The staff nurse will record the duration of surgery as time in minutes from incision to closure of the skin.

Blood Loss: The estimated blood loss will be determined by the increase in weight of sponges used during the operation, taking 1 gram equal to 1cc of blood and the number of subjects who received blood transfusion during operation.

Secondary Outcomes

Postoperatively, subjects will be assessed for urinary tract infection (UTI), micturition problems, and fistula formation during the hospital stay and for the next three months. Duration of catheterization and hospital stay will also be recorded. The outcome of each subject will be noted on a Performa by assigned medical officers during the hospital stay and the follow-up period and entered in SPSS20 datasheet.

1-Urinary tract infection (UTI) markers will be more than 10pus cells/hpf in urine or urine showing infectious organisms on culture on the third postoperative day.

- A. **Dysuria** will be expressed by the subject as painful micturition using an 11point Numeric Rating Scale ICCs (.673-.825), $r=.7-.99$. (0 No Pain, 1-3 Mild Pain, 4-6 Moderate Pain, 7-10 Severe Pain).
- B. **Other micturition problems** (feeling of incomplete evacuation, frequency, urgency, urethral and extra-urethral incontinence) will be measured subjectively on Likert scale questionnaire (0-never, 1-rarely, 2-sometimes, and 3-often) and analyzed as a composite variable in spss. Urinary retention will be diagnosed if post-micturition bladder volume is >50cc on ultrasonography on the day of discharge from the hospital.

- I. **Feeling of incomplete evacuation:** It is the feeling created by incomplete emptying of the bladder. The subject will be inquired about the feeling of full bladder accompanying it.
- II. **Urgency** will be diagnosed as a sudden urge to urinate.
- III. **Frequency** Needing to pass urine more than seven times in 24hours.

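### Operative time and blood loss, both primary, include the period before the mid-operation randomisation; this adds noise, not bias, and a time stamp and one extra sponge weighing would recover the precision

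*Combined protocol and SAP*

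**What the plan says.** The Outcome section makes both measures primary: "Primary outcomes will be the bladder injury rate, the extent of the injury, operative time, blood loss and proportion of subjects receiving blood transfusion". For operative time, "The staff nurse will record the duration of surgery as time in minutes from incision to closure of the skin". For blood loss, the rule is the "increase in weight of sponges used during the operation, taking 1 gram equal to 1cc of blood".

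Randomisation comes part-way through that interval. Under the second step of recruitment, when dense adhesions are met, "the primary surgeons will hold the operation and call the principal surgeon". The Adhesiolysis section has this surgeon grade the adhesions, after which "the Principal surgeon will enrol her in the study as subject and perform randomization into cystoinflation and control groups". Under Randomisation procedure, the theatre in-charge nurse opens the envelope at that point.

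Only then, and only in one arm, "the bladder will be retro-filled with 300cc saline by the assigned house officer". Control women stay on free catheter drainage. In either arm a suspected injury leads to a retrograde dye test, whose volume is not stated.

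The Entry Form has a single field for the time of operation. The Outcome Form lists operative time and blood loss twice, with no label to separate before from after. Neither form asks for a randomisation time or for a sponge weight at that moment.

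**The concern.** The time and bleeding between skin incision and the opening of the envelope cannot be changed by the allocated arm, yet they count in full in both outcomes. This period is likely to vary. The perioperative criteria allow the adhesions to be met at entry to the peritoneum or later, before the bladder flap, and the wait for the principal surgeon is not standardised. The intervention acts on a scale of minutes: 300cc at 60cc per minute takes 5 minutes to instil. Differences of a few minutes in opening and waiting could therefore blur the effect that the trial looks for.

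A second, separate matter is what the sponges absorb. Every gram counts as blood, and no rule deals with saline, dye, urine or amniotic fluid. If a bladder holding 300cc is perforated, some of that fluid could be recorded as blood loss in the cystoinflation arm.

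**Working it through.** **The plan's own figure.** The only design figure is 107 per group (Sample size), obtained from a calculator for proportions. No SD, target difference or power is stated for operative time or blood loss, so there is nothing to reproduce. The results below are conditional on assumed ratios.

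**Noise from the period before the envelope.** Write the outcome as A + B, with A before and B after the envelope. Set the SD of B to 1, the SD of A to r, and their correlation to ρ. The variance of the whole-operation outcome is 1 + r² + 2ρr. After adjustment for A as a covariate, the residual variance is 1 − ρ². The share of information lost by not adjusting is therefore

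loss = 1 − (1 − ρ²)/(1 + r² + 2ρr).

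With ρ = 0 this is r²/(1 + r²):

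- r = 0.25: 0.0625/1.0625 = 0.059, about 6%; 107 per arm act like 107 × 0.941 = 101.
- r = 0.5: 0.25/1.25 = 0.20, or 20%; 107 act like 107 × 0.80 = 86.
- r = 1: 1/2 = 0.50, or 50%; 107 act like 54.

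The 107 includes a 10% dropout allowance. With 107 × 0.9 = 96 analysed, the first two cases become about 91 and 77.

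In terms of power, 107 per arm give 80% power for (1.96 + 0.842) × √(2/107) = 0.383 SD of B. For the same effect measured over the whole operation, power is 76%, 71% or 51% when 10%, 20% or 50% of the total variance arises before the envelope.

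**Dependence on ρ.** At r = 0.5:

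- ρ = −0.25: total variance 1 + 0.25 − 0.25 = 1.00; loss = 1 − 0.9375/1.00 = 6%.
- ρ = +0.3: total variance 1 + 0.25 + 0.30 = 1.55; loss = 1 − 0.91/1.55 = 41%.

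Compared with simply replacing the outcome by B, unadjusted, the corresponding losses are 1 − 1/1.00 = 0% and 1 − 1/1.55 = 35%. Covariate adjustment is thus at least as precise as changing the outcome.

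**Bias.** A simulation assumed an SD of 7 minutes before and 10 minutes after randomisation, and a true difference of −5 minutes. The mean estimate was −4.99 under either definition. The standard error was 1.69 for the whole operation and 1.38 for the part after randomisation.

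**Fluid counted as blood.** Retro-fill follows the envelope, and women with an injury before enrolment are excluded, so any leaked retro-fill falls wholly in the later sponge weight. The excess in the arm mean is perforation rate × leaked volume. The rates below are assumptions: 1.17% and 4.49% are the Background's bladder injury rates for fourth and sixth caesareans, not perforation rates in dense adhesions, and 10% is illustrative.

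| Assumed rate | 50cc leaked | 300cc leaked |
|---|---|---|
| 1.17% | 0.6cc | 3.5cc |
| 4.49% | 2.2cc | 13.5cc |
| 10% | 5cc | 30cc |

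In a simulation with a 300cc leak, the false excess at 5% was 14.9cc for the whole operation and 14.8cc for the part after the envelope; at 10% it was 31.2cc and 30.6cc. Splitting the weight leaves it unchanged.

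**The case against.** The strongest reply is that incision-to-closure is objective and conventional, that the period before the envelope has the same expectation in both arms, and that the effectiveness criterion in the Project summary concerns bladder injury alone. All of that stands. It is why this is an improvement to be offered and not a flaw in validity, and why the reported definition should stay.

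The size is also open to challenge. No SD is given, and the result moves with the correlation. A reader might infer from r = 1 that half the trial's information is wasted. That would need opening and waiting to vary as much as adhesiolysis, delivery, any repair and closure together, and nothing in the documents supports it.

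A reader might also infer that sponge weights in the cystoinflation arm routinely contain saline. The documents do not say so: an intact bladder drains to the urine bag. A leak needs a full-depth perforation while the bladder is full, and the plan also counts injuries with intact mucosa. Dye-test fluid can arise in either arm.

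Finally, setting aside wet sponges may look like the natural cure. Theatre staff know the allocation, those sponges also hold blood, and the exclusions would fall mainly in one arm. That could replace a small error against cystoinflation with one in its favour.

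**Conclusion.** The point holds as a matter of precision. Two primary outcomes carry variation that arises before randomisation, and the forms do not capture what is needed to remove it. With uncorrelated parts and an SD ratio of 0.25 or 0.5, the loss is about 6% or 20% of the information, and more at a higher ratio; both the ratio and the zero correlation are assumptions. The comparison is not biased by this, provided that allocation is sound.

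The fluid question is separate and conditional. Retro-fill could add at most 300cc in one woman, and the arm mean shifts by the assumed perforation rate times the leaked volume, in the direction against cystoinflation. It would be wrong to conclude that the time stamp or the split weight deals with it.

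**What to change.** Add a field for the clock time at which the envelope is opened, and state that the existing time-of-operation field means the clock time of skin incision. Keep incision-to-closure as the reported operative time, and enter incision-to-envelope minutes as a covariate in the regression that the Statistical analysis section already plans without naming covariates.

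For blood loss, put aside the sponges used so far before the envelope is opened, weigh them once, and use that weight as a covariate. The total over the whole operation stays the reported outcome. Fixing both values before the allocation is disclosed keeps them independent of the arm.

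Keep all sponges in the main analysis. As a sensitivity analysis only, report blood loss with and without women who had a perforation or a dye test. Depth of injury is already on the Outcome Form; a yes/no box for the dye test is not, and would be needed. Removing these women also removes real bleeding and selects on events after randomisation, so the result should not replace the main one.

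The main change costs one form field and one extra weighing by staff already in theatre; the sensitivity analysis adds one tick box. If the time and weight are not taken during surgery, they cannot be reconstructed.

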- IV. **Vesicovaginal or uretro-vaginal Fistula:** In subjects with the complaint of urinary incontinence, the fistula formation i.e. abnormal communication of urinary bladder or ureter with vagina will be ruled out by three swab test and retrograde cystography. The follow up of fistula cases is outside the scope of this study so it will not be included in description or analysis.

C. **Duration of Foleys catheter and hospital stay:** The Foley's catheter will be removed after 24 hours in distension arms of both groups and subjects stay in the hospital for four days. In the bladder injury arms, the catheter will be kept in situ for 7days to give rest to the bladder for the healing of repair of muscularis disruptions, for 10 days in case of repair of perforations smaller than 1cm, and for 14 days for repair of perforations greater than 1cm. After removal of the catheter, the subjects will be kept in the hospital for twelve hours and then discharged if there will have no subjective urinary complaint.

The finding of subjects will be noted on output form by assigned trainees. The participant's first entry on follow up form will be completed on the third postoperative day; second entry will be at the time of discharge from the hospital and last entry at the end of three months postoperative period. In between, they will be advised to visit our team whenever a problem emerges during the postoperative period and their findings will be recorded on the output form. In subjects complaining of urinary incontinence, the fistula formation will be ruled out first by three swab test and then by retrograde cystography. The postoperative visit at the end of 3months will be mandatory. During this visit, all the subjects will be analyzed for postoperative micturition problems and their retrograde cystography will be performed to rule out fistula formation. The subjects with fistula will be referred to the urologist for further management. The last entry at the end of three months will also be mandatory for the inclusion of participant outcome after discharge in results. The participants will be advised to visit the researcher team at the end of 3months period. They will be reminded for their visit on phone call after week if they do not come for follow-up (See [Outcome](#)).

Statistical analysis

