The results of this study will be submitted for publication to an international, peer-reviewed journal, regardless of whether the results are positive, negative or inconclusive concerning the study hypothesis. Authorship eligibility will be based on the recommendations from the International Committee of Medical Journal Editors (ICMJE).

Perspectives of the study

This study is a small, single centred controlled trial. It is among one of the initial studies to test cysto-inflation to prevent bladder injury. If cysto-inflation proves significantly effective in this study, the evidence provided by this study will not be enough in this era of evidence-based medicine. Nevertheless, this research can serve as a foundation to initiate a much larger high-quality multicentre trial in the support of cysto-inflation to prevent bladder injury. This technique if proved effective can also be useful in all fields of pelvic surgery especially urology, urogynecology, and general surgery.

Potential Risks

- Participation in this study poses a risk for breach of confidentiality.
- Catheterization procedure is mandatory in this study. Approximately two out of hundred women may develop a bladder infection. The researchers will use proper sterilization and clean procedure of the insertion of the catheter according to the study protocol to minimize the risk of developing a bladder infection.
- Subjects of the study should not take part in more than one study at the same time as the outcome of the study can be disturbed by this approach.

Problems Anticipated during the study:

- If recruitment of subjects will not be complete during the anticipated study period, then the period of study may be extended from three months to one year or any further time till the recruitment of study is complete.
- In case of any unexpected outcome that may endanger the subject physically or psychologically, the study may be stopped any time.
- As the study is non-funded, the subjects will not be paid for participation in the study. The subjects belonging to the poor socioeconomic group and coming from distant areas will need thorough counselling for compliance to follow up visits.

Acknowledgements: Theatre staff helping in cysto-inflation study will be acknowledged in the publication.

Project Management:

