[name] is the Corresponding Author and chief investigator. She has conceived the project and she will write and review the manuscript and will create Figures and tables. She will hold a monthly meeting of the research team to evaluate any difficulties encountered with study design and to find a solution to the problems.

[name] will counsel the subjects, participate in preparing random numbers file, conduct surveys to collect preoperative and postoperative data in wards, participate in Manuscript writing and review the manuscript.

[name] will counsel the subjects, participate in preparing random numbers file, manage cysto-inflation in theatre, perform follow up of the subjects and conduct the survey in the hospital to collect data after discharge, and will review the manuscript.

[name] will collect all preoperative and postoperative data, enter it into SPSS data sheet and hand it over to statistician and review the manuscript.

[name] will perform statistical calculations and will review the manuscript.

Collaboration with other scientists: To avoid Bias, the research team will shift data in spss datasheet to [name] for the compilation of results on an individual level.

A randomized controlled trial of CystoInflation to prevent bladder injury in the adhesive disease of multiple caesarean sections

ENTRY FORM OF CYSTOINFLATION STUDY

Country	Pakistan
Hospital	Lady Willingdon Hospital
Unit	1

Patient Profile

Patient name	
Age	
Gestational age	
Parity	
Socioeconomic status	
BMI	

Examination

Pulse	
BP	
Temperature	
Pallor	
Chest	
CVS	
P/A	

Investigations

Blood Group	
C/E blood	
C/E Urine	
BSL(F)	
Obstetric USG	

Randomization

Date of operation	
Time of operation	
Grade of adhesions	
Eligible	
Consent for study	
Random number	
Signature of the Principal	

surgeon	
---------	--

- Store the original completed form in the Principal investigator study file.

A randomized controlled trial of Cysto-inflation to prevent bladder injury in the adhesive disease of multiple caesarean sections

OUTCOME FORM

Operative Findings

Bladder injury	No	Yes
Size		
Site		
Depth		
Operative time		
Blood loss		
blood transfusion		
Operative time		
Blood loss		
blood transfusion		

Postoperative Follow up on 3rd postoperative day

Follow up	No	Yes
WBC count		
Urine culture	_ive	+ive

fever	No					Yes					
Dysuria	0	1	2	3	4	5	6	7	8	9	10
Frequency of micturition	0				1			2			3
Urgency of micturition	0				1			2			3

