Feeling of urinary retention	0				1			2			3
Urethral incontinence	0				1			2			3
fistula	No					Yes					

Postoperative Follow up on the day of discharge from hospital

Follow up	No					Yes					
Postoperative Postmicturition bladder volume											
fever	No					Yes					
Dysuria	0	1	2	3	4	5	6	7	8	9	10
Frequency of micturition	0				1			2			3
Urgency of micturition	0				1			2			3
Feeling of urinary retention	0				1			2			3
Urethral incontinence	0				1			2			3
fistula	No					Yes					

Postoperative Follow up from 1-6weeks

Came for follow up	No					Yes					
fever	No					Yes					
Dysuria	0	1	2	3	4	5	6	7	8	9	10
Frequency of micturition	0				1			2			3
Urgency of micturition	0				1			2			3
Feeling of urinary retention	0				1			2			3
Urethral incontinence	0				1			2			3
fistula	No					Yes					

Postoperative Follow up from 6weeks -3months

Came for follow up	No					Yes					
fever	No					Yes					
Dysuria	0	1	2	3	4	5	6	7	8	9	10
Frequency of micturition	0				1			2			3
Urgency of micturition	0				1			2			3
Feeling of urinary retention	0				1			2			3
Urethral incontinence	0				1			2			3
fistula	No					Yes					

Follow up at the end of 3months

Came for follow up	No					Yes					
fever	No					Yes					
Dysuria	0	1	2	3	4	5	6	7	8	9	10
Frequency of micturition	0		1		2		3				
Urgency of micturition	0		1		2		3				
Feeling of urinary retention	0		1		2		3				
Urethral incontinence	0		1		2		3				
Fistula confirmed by retrograde cystography	No					Yes					

Figure 1:

[figure not shown]

Figure1. Consort Diagram. Patient assignment to groups, follow up and analysis

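### Urinary infection is to be assessed for three months, but only a day-3 urine result can count as an infection

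*Combined protocol and SAP*

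**What the plan says.** The opening sentence of Secondary Outcomes sets one window for three outcomes: "subjects will be assessed for urinary tract infection (UTI), micturition problems, and fistula formation during the hospital stay and for the next three months". Item 1 of that section then gives the only definition of urinary infection in the document: "Urinary tract infection (UTI) markers will be more than 10pus cells/hpf in urine", or "urine showing infectious organisms on culture on the third postoperative day".

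The Outcome Form has five follow-up blocks. The block headed "Postoperative Follow up on 3rd postoperative day" holds a WBC count (read here as the pus-cell count) and a urine culture. The next block, "Postoperative Follow up on the day of discharge from hospital", and the three after it have neither.

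Item C of Secondary Outcomes sets catheter time. Without bladder injury, as I read the wording, "The Foley's catheter will be removed after 24 hours in distension arms of both groups". With injury, it is 7 days for a muscular-layer repair, 10 days for a perforation under 1 cm, and "for 14 days for repair of perforations greater than 1cm".

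The only infection rate given is under Potential Risks, for catheterisation in general: "Approximately two out of hundred women may develop a bladder infection".

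**The concern.** A three-month outcome needs a definition and a data field that work beyond day 3. Here neither does. Women are told to come back with fever or urinary complaints, so later infections are likely to reach the study team, but the plan has no step that turns them into a counted infection.

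Two things are at stake. First, an infection rate that rests on day 3 alone could be taken as covering three months, because the section's opening sentence says it does. Second, the uncounted period is not the same for all women. It includes most of the catheter time of those with bladder injury, and bladder injury is the primary outcome. A comparison of infection between arms could therefore be distorted by the effect under study. Bladder infection is also the only bodily harm listed under Potential Risks.

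**Working it through.** The plan states no figure for this outcome, so there is none to reproduce. The check sets the passages side by side and then bounds the size.

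**1. Where an infection could be recorded**

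| Outcome Form block | Urine test or infection field | Other fields |
|---|---|---|
| Day 3 | WBC count, urine culture | Fever, dysuria, frequency, urgency, retention feeling, incontinence, fistula |
| Discharge | None | Same, plus post-micturition bladder volume |
| 1 to 6 weeks | None | Same as day 3 |
| 6 weeks to 3 months | None | Same as day 3 |
| End of 3 months | None | Same as day 3, with fistula checked by cystography |

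The text on the mandatory three-month visit names micturition problems and cystography, and no urine test. The Adverse events section has a separate register, with no link to the infection outcome. Followed exactly, the plan yields a day-3 infection rate and nothing later.

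**2. Day 3 against catheter removal** (durations from item C)

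- No injury: removed at 24 hours, so the test comes 3 − 1 = 2 days after removal.
- Muscular-layer injury: 7 − 3 = 4 days before removal.
- Perforation under 1 cm: 10 − 3 = 7 days before removal.
- Perforation over 1 cm: 14 − 3 = 11 days before removal.

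**3. Size at the protocol's own rate**

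Inputs: 107 women per arm (Sample size) and 2% (Potential Risks).

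- Expected infections per arm: 107 × 0.02 = 2.14. With the planned 10% dropout, 107 × 0.9 × 0.02 = 1.93.
- The share that appears after day 3, *s*, is not stated. Missed per arm = 2.14 × *s*, so *s* from 0 to 1 gives 0 to about 2.

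**4. How unequal the loss could be (illustration, assumed rates)**

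The documents give no injury rate for women with dense adhesions and no late-infection rate after injury. Assume control injury of 5% to 30%, halved by cystoinflation (the Project summary's own effectiveness threshold), and late infection in 10% to 50% of injured women.

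- Low end: long catheters in 107 × 0.05 = 5.35 control and 2.68 cystoinflation women. At 10%, about 0.5 and 0.3 infections go uncounted, a gap of 0.27.
- High end: 107 × 0.30 = 32.1 and 16.05 women. At 50%, about 16 and 8 go uncounted, a gap of about 8.

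The range is too wide to serve as an estimate. It shows only that the gap can run from negligible to larger than the 2 infections per arm implied by the 2%, a rate that is not specific to long catheter times.

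**The case against.** The strongest reply is that a specific definition follows a general sentence. The opening sentence covers three outcomes at once, and item 1 then dates infection to day 3. On that reading infection is a day-3 outcome, while micturition problems and fistula run to three months. A fixed laboratory test at one time in both arms is also a sound measure of infection from a filling done once, in theatre. This stands as a defence of the day-3 marker, and the marker should be kept. It does not remove the mismatch, because infection is named in the sentence that promises three months. The wording could also leave the pus-cell criterion undated, but the form has no place for a later count.

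Four stronger readings are tempting, and the documents do not support them.

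- *Later infections go unrecorded.* The later blocks record fever, dysuria, frequency, urgency, retention feeling, incontinence and fistula. The adverse-event definition covers any unwanted event that takes a woman to a practitioner or hospital. Late infections are missing from the infection outcome, not necessarily from the records.
- *Women with long catheters are unobserved.* They stay until twelve hours after catheter removal, so their discharge entry falls after the catheter period. What that entry lacks is a urine or infection field.
- *The day-3 rate will be published as a three-month rate.* Nothing in the plan says so. The wording leaves room for it.
- *The gap hides a harm of cystoinflation.* Long catheter times come from bladder injury, not from filling. If cystoinflation reduces injury, catheter-related late infections would be missed more in controls, which would work against cystoinflation. Late infections from the filling itself would be missed in the cystoinflation arm, so the net direction is not certain.

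**Conclusion.** The point holds as a mismatch between the stated window and the only definition and data fields: the plan cannot produce the three-month infection outcome that it names. This conclusion rests on the text and the form, not on any assumed rate.

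The size is unknown. At the protocol's 2% about 2 infections per arm are expected, and between 0 and about 2 per arm would go uncounted, depending on a share after day 3 that the documents do not give. A reader might infer that about half are missed; no figure in the plan supports that. With so few events, one uncounted case could create or remove an observed difference. Imbalance between arms is plausible because catheter time follows injury, but its extent depends on injury and late-infection rates that would have to be assumed.

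This is a minor point on a secondary outcome. It is worth settling because it is cheap to settle.

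**What to change.** - Keep the day-3 laboratory result as a separate outcome, labelled as day-3 urinary infection.
- Add one row to the discharge block and the three later blocks of the Outcome Form: *UTI diagnosed since last entry (yes/no, date, basis: urine result or clinician diagnosis)*.
- Cross-check that row against the adverse-event register before the data go to the statistician.
- Report the day-3 rate and the cumulative three-month rate separately, by arm. The Statistical analysis rule that a repeated problem is entered once already prevents double counting.

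The cost is one row in four form blocks, a sentence of definition and the register check. It needs no new visits and no routine cultures. Postoperative follow-up is already to be done by an officer unaware of allocation. The drawback is that later diagnoses are less standardised than a day-3 test and depend on who seeks care. That is why the basis of diagnosis is recorded and the two rates are kept apart.

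If the sponsor prefers not to add the row, the alternative is to reword the opening sentence of Secondary Outcomes so that the infection window ends at day 3. A day-3 rate then cannot be presented as a three-month result.
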